5.3.5 Supplemental Analysis

Two methods will be applied for the rescoring of mICARS, Rescored mICARS Method 1 (see Appendix II) and Rescored mICARS Method 2 (see Appendix III). In each case, the rescored mICARS will be analyzed using the MMRM methods as for the primary analysis of mICARS. The nominal p-value will be presented, and no adjustments for multiplicity will be made.

5.3.6 Sub-group Efficacy Analysis

All summarization and analysis of efficacy data during the extension period will be considered exploratory.

The primary efficacy analysis will be repeated for region (India; Europe, Australia, Israel, and Tunisia; United States), age sub-group (6 to <10 years, ≥10 years), sex (male, female), adjudicated genetic disease characteristics, the subset of subjects having a confirmed diagnosis of AT, and baseline disease severity (mild or severe, as determined by an independent adjudication committee).

5.4 Safety Analysis

Safety analysis will be performed for the safety population, unless otherwise noted. No statistical comparisons between groups will be performed.

5.4.1 Adverse Events

Adverse events (AEs) will be coded using MedDRA version 19.0. Coding will include system organ class and preferred term. All verbatim descriptions and coded terms will be listed for all AEs.

Adverse events of special interest include those which are potentially steroid related and those indicative of adrenal insufficiency. These will be summarized separately.

If the assessment of seriousness is missing for an event, then the event will be considered serious as a worst case. The same rule will be applied in case of missing relationship data (the worst relationship will be assumed) and missing severity data (severe will be assumed).

Each AE recorded on the CRF will be classified as either a pre-treatment AE or a treatment-emergent AE (TEAE). Adverse events occurring >60 days after the last dose of study drug will not be considered treatment emergent.

Pre-treatment AEs

Pre-treatment AEs will be defined as AEs that started and either stopped before the first infusion of study treatment or continued after and did not worsen in intensity during the treatment period. Any pre-treatment AEs identified will not be summarized by system organ class and preferred term but they will be flagged on all listings of AEs (all AEs and serious AEs).

Treatment-emergent AEs

Each adverse event will be classified as treatment emergent or not during one of three treatment periods:

- The initial treatment period (Period 1), defined as the day of the first infusion through the day just prior to the day of the Visit 9 (“Month 6”) infusion, or ≤60 days after last dose if the subject never continued past this period;
- The Visit 9 (“Month 6”) to Visit 12 (“Month 9”) period (Period 2), defined as the day of the Visit 9 (“Month 6”) infusion through the day just prior to the day of the Visit 12 (“Month 9”) infusion, or ≤60 days after the last dose if the subject never continued past this period; and
- The Visit 12 (“Month 9”) to Visit 15 (“Month 12”) period (Period 3), defined as the day of the Visit 12 (“Month 9”) infusion through 60 days after the last dose.

AEs starting on or after the date/time of the first infusion of a period and prior to the date/time of the first infusion of the next period will be considered TEAEs during the period, for example:

- Events that started on the day of or after the first infusion and are not a continuation of a pre-treatment event.
- Events that started before the first infusion and worsened after the first infusion.
- Events with partial onset dates that indicate that the event could be treatment-emergent during the period.
- Events with completely missing onset dates.

For adverse event reporting, subject events will be allocated to the period of last treatment.

For each treatment period and over all periods, an overall summary of the number and percentage of safety population subjects having pre-treatment AEs and TEAEs will be presented by treatment received, along with the total number of TEAEs. This summary will also include the number and percentage of subjects with related TEAEs, serious TEAEs, serious related TEAEs, TEAEs leading to discontinuation, and TEAEs leading to death. Only subjects treated during the period of interest will be included in the denominator for percentages. For the summarization of AEs over all periods, treatments summarized will include EDS-EP low dose and high dose groups, non-switch placebo, placebo pre-switch, and each active treatment post-switch; placebo subjects who switch to active treatment will have only adverse events emergent during active treatment summarized.

TEAEs will also be summarized as the number and percentage of safety population subjects treated during the period (or the study overall) having any event and any event by MedDRA system organ class and preferred term. For each subject, multiple occurrences of the same event will be counted once within a system organ class and preferred term. Summaries will be prepared for the following types of events:

- TEAEs
- Related TEAEs
- Serious TEAEs
- Related Serious TEAEs
- Potentially steroid-related TEAEs
 - Low bone mineral density
 - Low CD4 count
 - Itching
 - Osteopenia
 - Osteoporosis
 - Weight gain
 - Cortisol suppression
 - Glaucoma
 - Stunt growth
 - Infections
 - Hyperglycemia
- TEAEs indicative of adrenal insufficiency per Protocol Appendix 12 and monitored by a data safety monitoring board
- TEAEs leading to discontinuation
- TEAEs leading to death
- TEAEs by maximum severity
- TEAEs by worst relationship

This summarization will be repeated for Continuous Exposure 2 subjects, and for subjects whose treatment was ended due to COVID-19.

For subjects with treatment interruptions that result in gaps in dosing of greater than 60 days, adverse events will only be considered treatment emergent if they occur within 60 days following the last dose. Adverse events that occurred greater than 60 days following the last dose will not be considered treatment emergent. For this population of subjects (those with long treatment interruptions), and for the sub-population whose long treatment interruption was due to COVID-19, three types of summarization will be prepared:

- On dose (treatment emergent) adverse events – summarized by treatment being taken at the initiation of the interruption
- Off dose (not treatment emergent) adverse events – summarized by treatment being taken at the initiation of the interruption
- Restart (TEAE after restart of treatment) adverse events – summarized by treatment taken when restarted

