11.6 Laboratory Sample Collection

Revised study procedures to ensure sterility of the EDS-EP

New aseptic procedures have been implemented to ensure sterility during blood collection for the EDS process, the various steps of the EDS process, sample collection for routine laboratory tests, sample collection from the EDS-EP for sterility testing, and administration of the EDS-EP to the patient. Details of these procedures are described in a separate document entitled “Revised Study Procedures on Sterility Testing for Study IEDAT-02-2015 (ATTeST)”, which will be provided to each site (see [Appendix 13](#)). These new procedures include the following measures that must be performed to ensure sterility:

- Blood sampling under sterile conditions.
- Careful hand washing and use of fresh (non-sterile) gloves for each patient, disinfected frequently using a bactericidal rub.
- Frequent and repeated use of a bactericidal solution, including the mandatory use of 2% chlorhexidine in 70% isopropyl alcohol for disinfection of the skin at the venipuncture site, or

Version 1.0, 09May2015; Version 2.1, 16Nov2015; Version 3.0 (Amend. 1), 01Feb2016; Version 3.1 (Amend. 2), 28Apr2016; Version 3.2 (Amend. 3), 25May2016; Version 4.0 (Amend. 4), 29Nov2016; Version 5.0 (Amend. 5, Site-specific), 20Sep2017; Version 6.0 (Amend. 6), 29Sep2017; Version 7.1 (Amend. 7.1), Final 13 March 2018, Version 8.0 (Amend. 8.0), Final 23 April 2018; Version 10.0 (Amend. 10), Final 16 April 2019; Version 11.0 (Amend. 11), Final 24 Jun 2020

during handling of the venous catheter (if used), and for disinfecting ports, connectors and working surfaces/environments.

- CCI [REDACTED]
- [REDACTED]
- [REDACTED]
- [REDACTED]
- [REDACTED]
- [REDACTED]
- [REDACTED]
- [REDACTED]
- [REDACTED]

Blood sampling

Venous blood samples will be drawn for routine safety evaluations (hematology and clinical chemistry). The maximum volume of blood drawn for laboratory analyses on any one day will be approximately 68 ml:

- 1.0 mL for hematology tests [Screening, Day 0 (optional) and Months 3, 6, 9 and 12]
- 5.0 mL for clinical chemistry [Screening, Day 0 (optional) and Months 6 and 12]
- 3.5 mL for clinical chemistry [Day 0 (optional) and Months 3 and 9]
- 1.0 mL for CD4+ lymphocytes tests (Screening, Day 0, Month 6 (pre-dose), and Month 12); samples for alpha fetoprotein, C-reactive protein, and Hb1Ac to be taken at same timepoints from blood collected for clinical chemistry or hematology.

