14.1.2 Data Collection

For each event, record the following information on the Adverse Event section of the Case Report Form:

- **Classification of the Event:** Classify the event as either serious or non-serious
- **Description of Signs or Symptoms:** Whenever possible, record a specific diagnosis for the event. If a diagnosis cannot be made, then record each sign or symptom separately, e.g., record nausea and vomiting as two events. If multiple episodes of an event occur, separated by an appropriate time interval to justify considering the subsequent episodes as a repeat occurrence, record each episode separately on the Case Report Form.
- **Onset Date and Time:** Record the date and time the event started. If a change from baseline/previous evaluation in a laboratory test is reported as an adverse event, record the start date as the date of collection of the first lab sample that shows the change.
- **Stop Date and Time:** Record the date and time the event resolved. If a change from baseline/previous evaluation in a laboratory test is reported as an adverse event, record the stop date as the date of collection of the first sample that shows a return to the previous level.
- **Intensity:**
 1. **Mild:** Event not resulting in disability/incapacity, which resolves without treatment.
 2. **Moderate:** Event not resulting in disability/incapacity, which requires treatment.
 3. **Severe:** Event resulting in temporary and mild disability/incapacity, which requires treatment.
- **Relationship to the Study Agent:** Every effort should be made to determine the cause of each adverse event. The correlation between the study agent and the adverse event should be classified as follows:
 1. **Probable**
 - a) The event follows a reasonable temporal sequence from administration of the study agent;
 - b) The event follows a known response pattern to the study agent;
 - c) The event cannot be reasonably explained by:
 - the known characteristics of subject's clinical state, or
 - by other therapy administered, or
 - by the diagnostic/interventional procedure;
 - d) There is evidence of partial or complete disappearance of the event after withdrawal of the product (positive de-challenge)

2. **Possible**
- a) The event follows a reasonable temporal sequence from administration of the study agent;
 - b) Causation of the event by the study agent cannot be excluded;

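### SAP 5.4.1 gives two conflicting boundaries for the adverse-event periods, so a finding made before the Visit 9 or Visit 12 infusion on the same day has no settled period and, for placebo switchers, no settled treatment.

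*SAP*

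**What the plan says.** SAP Section 5.4.1 assigns each adverse event to one of three periods. By the bullets, Period 1 is "defined as the day of the first infusion through the day just prior to the day of the Visit 9" infusion. Period 2 runs from the day of the Visit 9 "infusion through the day just prior to the day of the Visit 12" infusion. Period 3 runs from the day of the Visit 12 "infusion through 60 days after the last dose". A patient who never continues past Period 1 or 2 keeps events in that period for up to 60 days after the last dose.

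The next sentence sets a different boundary. It counts as treatment-emergent in a period "AEs starting on or after the date/time of the first infusion of a period and prior to the date/time of the first infusion" of the following period. Its first example returns to whole days. Further on, the section says that "subject events will be allocated to the period of last treatment".

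Protocol Section 14.1.2 asks for the date and time of onset in general. For a laboratory change reported as an adverse event, however, it tells the site to "record the start date as the date of collection of the first lab sample that shows the change" and mentions no time. The synopsis puts the Month 3, 6, 9 and 12 assessments ahead of dosing. Section 11.2 gives the Visit 9 order as evaluations, blood draw for processing, then infusion.

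**The concern.** A Month 6 or Month 9 finding made on the morning of the infusion is an observation on the treatment just completed. Under the day bullets it belongs to the next period. Under the clock-time sentence it stays where it arose. A programmer cannot satisfy both, and the SAP does not say which prevails.

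Two things are at stake. First, Period 1 is the only period in which the whole placebo arm is on placebo, so its adverse-event tables are the main controlled safety display. Losing Month 6 laboratory events from those tables for patients who continue, while keeping them for patients who stop, makes the content depend on continuation. Second, Visits 9 and 12 are where placebo patients switch. Moving an event forward across a switch also moves it from placebo to EDS-EP.

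**Working it through.** **1. Reproduce the planned switching (SAP Section 5.2.4, Table 5; SAP Section 5.1.8).** Of 60 placebo patients, 60 × 1/3 = 20 switch at Visit 9 (10 per dose), leaving 40. Then 40 × 1/2 = 20 switch at Visit 12 (10 per dose), leaving 20. This matches Table 5, which assumes no dropout.

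**2. Classify one event under each rule.** Take a sample at 08:00 and an infusion at 13:00 on the Visit 9 day.

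| SAP 5.4.1 rule | Onset time recorded | Onset date only |
|---|---|---|
| Day bullets | Period 2 | Period 2 |
| Clock-time sentence | Period 1 | Not determined |
| Last-treatment sentence | Period 1 if it means the last treatment before onset; a later period if it means the last period treated | Same ambiguity |

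At Visit 12 the choice is between Period 2 and Period 3 in the same way. Period 3 has no later infusion to bound it, so its end is not in question.

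**3. Which rule is likely to govern laboratory events.** With only a collection date, the clock-time sentence cannot be evaluated and the day bullets can. SAP Section 5.2.5 also ends the initial period for concomitant medications on the day before the Visit 9 infusion. The day boundary therefore looks like a convention of the SAP. This is an inference; the documents do not settle it.

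**4. Which findings are exposed.** Protocol Section 11.6 schedules "CD4+ lymphocytes tests (Screening, Day 0, Month 6 (pre-dose), and Month 12". Screening and Day 0 precede treatment, so the pre-dose Month 6 sample is the only scheduled on-treatment CD4 test of the initial period. For continuing patients, Protocol Section 11.4.11 takes it from the diverted blood, which ties it to the day of processing and infusion. Low CD4 count is on the SAP's list of potentially steroid-related events. Month 9 has no scheduled CD4, HbA1c or bone density test. The exposure there is routine laboratory tests, ECG, the hemolysis panel and examinations.

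**5. Who is affected under the day rule.**
- Continuing on the same treatment: the event moves from Period 1 to Period 2 (or 2 to 3); the treatment label is unchanged.
- Stopping at or before Month 6: the event stays in Period 1 if it is within 60 days of the last dose.
- Placebo switched at Visit 9 or 12: the event moves to the next period and to EDS-EP. In the laboratory tables the same value is the patient's pre-switch baseline (Baseline 2, SAP Sections 5.4.2 and 5.4.6).

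**6. Size.** Patients whose treatment label can be wrong: 20/180 = 11.1% at each switch and 40/180 = 22.2% in all. With 175 randomized, and assuming equal thirds, placebo is 175/3 = 58.3 and each switch involves 58.3/3 = 19.4.

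Effect of one misassigned event, by how the column is built:
- One dose, one switch visit: 1/10 = 10 points.
- One dose, both switch visits pooled, as the all-period summary suggests: 1/20 = 5 points.
- Switchers pooled with their dose's randomized arm in Period 2: 1/(60 + 10) = 1.4 points.
- For comparison, a 60-patient placebo column: 1/60 = 1.7 points.

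The documents give no rate for such events, so the expected number cannot be stated.

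**The case against.** The strongest reply is that the clock-time sentence already gives the right answer, that the case report form collects onset time, and that the last-treatment sentence, read naturally, agrees. All of this is fair. It means the defect is a contradiction. A reader might infer that the SAP definitely places every pre-infusion finding in the wrong period; the text does not support that. But the reply does not remove the day bullets, which are the formal definitions, and it does not help where a laboratory onset has no time.

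It is also fair that the reach is limited. Laboratory and ECG results are summarized by visit, with shift tables for the initial treatment period. A reader might infer that the Month 6 three-arm comparison disappears; it does not, because those tables still show it. The whole-study adverse-event tables keep the events in the randomized low- and high-dose columns. A laboratory abnormality becomes an adverse event only on the investigator's judgement (Protocol Section 13.4). Several analytes, such as creatinine and the blood count, are also tested earlier in the initial period. SAP Section 5.4 plans no between-group safety tests.

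A reader might also infer that findings made on Day 1 before the first infusion become treatment-emergent. The definition of pre-treatment events in the same section largely covers them, because it refers to events starting before the first infusion and not before its calendar day.

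**Conclusion.** SAP Section 5.4.1 contains two boundaries that give opposite results for a finding made before the Visit 9 or Visit 12 infusion on the same day. The contradiction is certain. Its effect depends on which rule is programmed and whether an onset time exists.

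If the day rule governs, Month 6 laboratory events, low CD4 among them, leave the Period 1 adverse-event tables for patients who continue and remain for those who stop. For the planned 20 placebo switchers at each of Visits 9 and 12, findings made on placebo appear under EDS-EP. One event is worth between 1.4 and 10 points, depending on the column layout. It would be wrong to conclude that treatment is miscredited for everyone: patients who stay on their treatment change period only. By-visit laboratory and ECG tables, alpha and power are untouched. The change should be made, because it affects the content of the main controlled adverse-event tables and costs little.

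**What to change.** In SAP Section 5.4.1, delete the wording that ends Periods 1 and 2 on the day before the infusion, and make the date and time of the Visit 9 and Visit 12 infusions the single boundary. State that the last-treatment sentence means the last infusion before onset.

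Add a fallback for date-only onsets. If that date is the Visit 9 or Visit 12 infusion day, and the event was first shown by an assessment scheduled before the infusion, assign it to the preceding period and treatment. The adverse-event fields listed in Protocol Section 14.1.2 include no link to a sample, so these cases should be identified individually and agreed at the blinded data review meeting.

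The cost is SAP wording, minor programming and a short case review before database lock. No new data are needed.

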	
As a results of the COVID-19 pandemic, temporary changes to the protocol have been implemented. These changes are described in Appendix 14. Patients who are not experiencing severe side-effects, or have deteriorated significantly while on the treatment and provide informed consent will be eligible to continue treatment for an additional 6 months in a double-blind, placebo-controlled extension treatment period (or longer, in case a patient is willing to be enrolled in the open-label study IEDAT-03-2018, but the study has not yet received IRB/EC approval at the time the patient reaches Visit 15/Month 12). Patients meeting all entry criteria will be treated as follows:
 
 • Patients originally randomized to EDS-EP treatment groups (Group 1 or Group 2) will continue on the same treatment; • Patients originally randomized to the Placebo group (Group 3) will be re-randomized in equal proportions (1:1) to receive either the EDS-EP ~5-10 mg DSP/infusion or ~14-22 mg DSP/infusion, as follows: 
 ○ Following 6 months of treatment, one third of the originally randomized placebo patients will be re-randomized to treatment with EDS-EP, as described above; ○ After 9 months of treatment, one third of the originally randomized placebo patients will be re-randomized to treatment with EDS-EP, as described above; ○ At 12 months, all remaining placebo patients who continue open-label treatment will receive treatment with EDS-EP, as described above. 
The ICARS will be administered by a site rater and scoring verified by a central remote qualified rater, based on a video recording of the assessment at the site. The scores provided by the central remote raters will be used for the primary analysis of the ‘Modified’ ICARS (primary efficacy endpoint). The site ICARS rater will not be involved in the rating of the CGI-S and CGI-C, VABS, QoL or A-T NEST scale. The CGI rater will not have access to the ICARS ratings, but may refer to other scales in scoring the CGI.
 
All patients who complete 12 months of treatment in the trial, complete the study assessments, and provide informed consent will be eligible to continue treatment with EDS-EP in an open-label, extension study (IEDAT-03-2018). In case a patient is willing to be enrolled in the open-label study IEDAT-03-2018, but the study has not yet received IRB/EC approval at the time the patient reaches Visit 15/Month 12, the patient may undergo unscheduled monthly assessments/infusions (according to the assigned blinded treatment) starting from the time Visit 15/Month 12 should be performed, and continuing until the site has been initiated for the open-label study IEDAT-03-2018 and he/she has been evaluated for eligibility for the study. All patients, including those previously treated with placebo, who meet all of the selection criteria will receive monthly infusions of EDS-EP (dose range of ~14-22 mg DSP/infusion).

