- Patients originally randomized to the Placebo group (Group 3) will be re-randomized (randomization to be done at baseline) in equal proportions (1:1) to receive either the EDS-EP ~5-10 mg DSP/ infusion or ~14-22 mg DSP/infusion (or the remaining dose of EDS-EP, if one of the doses has been eliminated following the Interim Analysis), as follows:
 - Following 6 months of treatment, one third of the placebo patients will be switched to treatment with EDS-EP, as described above;
 - After 9 months of treatment, one third of the placebo patients will be switched to treatment with EDS-EP, as described above;
- At 12 months, all remaining placebo patients who continue in the open-label phase will receive treatment with EDS-EP, as described above.

Visit 9 (Month 6) evaluations from the Initial Treatment Period will serve as the Baseline assessments for the Extension Treatment Period. Once these are completed, patients will have blood drawn for the EDS encapsulation procedure and will receive the infusion as before. Vital signs and a physical examination will be performed after dosing.

Subsequently in the Extension Treatment Period, EDS-EP infusions will be performed at Months 7, 8, 9, 10 and 11 (Visits 10 – 14), after which vital signs (including body weight and height in triplicate) and a physical examination will be performed. The C-SSRS assessment will also be performed at each of these visits. A blood sample will be collected for measurement of serum creatinine at Months 7, 8, 10 and 11, whereas creatinine will be part of the routine laboratory tests at Months 9 and 12. In addition, on Month 9 (Visit 12), all efficacy assessments (ICARS, CGI-C, CGI-S, VABS, and QoL) will be done prior to the infusion, and the neurological examination, routine laboratory tests and the ECG will be repeated. Upon completion of the EDS process 2.5 mL of the processed blood will be collected for measurement of DSP concentration and a CBC.

At Months 6 and 9, in selected centers, a 5-mL sample will be taken from the EryKit_01 bowl at the end of the process to assess RBC osmotic resistance. At Months 6 and 9, a hemolysis panel will be done pre- and post-infusion.

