11.5.6 Safety Follow-up Visit (Visit 16)

All patients who discontinue prematurely, as well as those who complete the 12-month treatment period but do not continue treatment in the open-label extension study, will be required to return for a Safety Follow-up Visit (Visit 16) 30 days after their final assessment or at least 60 days after their last infusion, whichever is longer. At this visit, A-T NEST will be administered and the occurrence of any AEs or Serious AEs (SAEs) reported by the patient/caregiver or observed by the Investigator since the previous visit will be recorded.

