14 REPORTING SAFETY INFORMATION

14.1 Adverse Events

Assessment of Adverse Events (AEs) will be performed throughout the study, from the time of signing of the ICF at the start of the Screening period through the final study visit (Month 12 or early discontinuation). All Adverse Events will be recorded in the CRF. In addition, all subjects will be followed up through 30 days after the final visit (Month 12 or early discontinuation) or at least 60 days after the final infusion, whichever is longer, for the occurrence of any AEs or SAEs.

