Visit 14	330	Not before 21 days after the prior infusion (Infusion 11), +10 days
Visit 15	360	Not before 21 days after the prior infusion (Infusion 12), +10 days
Visit 16	390	30 days after subject final assessment or at least 60 days after their last infusion, whichever is longer

The schedule of assessments for the initial treatment period and extension treatment period is in [Appendix I](#).

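### SAP 5.4.1 does not cut adverse-event Period 3 at the first open-label infusion, so any event recorded in the overlap would be counted under placebo or low dose

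*SAP*

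**What the plan says.** SAP 5.4.1 states: "Each adverse event will be classified as treatment emergent or not during one of three treatment periods". Periods 1 and 2 close the day before the Visit 9 and Visit 12 infusions respectively. They carry a 60-day tail only for subjects who went no further. Period 3 has no such condition: it runs from the Visit 12 "infusion through 60 days after the last dose". The section's one general cut-off is that events starting "prior to the date/time of the first infusion of the next period will be considered TEAEs during the period". No fourth period is defined. The SAP Introduction describes Period 3 differently, as Visit 12 to Visit 15 (Month 12).

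On dosing, Protocol 11.2 says: "Subsequently in the Extension Treatment Period, EDS-EP infusions will be performed at Months 7, 8, 9, 10 and 11". No infusion is scheduled at Visit 15, whose window in SAP 1.3 is "Not before 21 days after the prior infusion (Infusion 12), +10 days". Protocol 7.3 makes placebo patients eligible for open-label EDS-EP at one year, and the Synopsis says: "All patients, including those previously treated with placebo, who meet all of the selection criteria will receive monthly infusions of EDS-EP".

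On follow-up after Month 12, the protocol says two things. Section 14.1 says "all subjects will be followed up through 30 days after the final visit (Month 12 or early discontinuation) or at least 60 days after the" (the 60 days count from the last infusion). Section 11.5.6 limits the Safety Follow-up Visit to early discontinuers and "those who complete the 12-month treatment period but do not continue treatment in the open-label extension study, will be required to return for a Safety" (the same visit). The Synopsis, 11.2 and 15.2 agree with 11.5.6.

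**The concern.** A 60-day tail after a Month 11 infusion reaches past Month 12, when a rollover patient may already be on open-label EDS-EP. SAP 5.4.1 reports non-switch placebo as its own group and separates pre-switch from post-switch events for the Month 6 and Month 9 switches. SAP 5.1.8 lists Month 12 as a third switch point, but 5.4.1 gives no cut there. As written, an event recorded after a non-switch placebo patient's first open-label infusion, and within 60 days of the last blinded one, is a placebo TEAE.

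Low-dose patients are affected in the same way, because Protocol 7.3 puts all open-label patients in the high dose range. For high-dose patients the dose range does not change, so attribution is not affected.

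At stake are the Period 3 and Entire Study adverse-event tables. SAP Table 5 plans only 20 non-switch placebo patients in Period 3, so one misattributed patient moves a placebo percentage by 1/20, or 5 points.

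**Working it through.** **Inputs**
- Target days (SAP 1.3): Visit 12 at 270, Visit 14 at 330, Visit 15 at 360, Visit 16 at 390.
- Infusion interval (Protocol 11.2): 21 to 28 days, with a +10-day visit window. The SAP's target-day grid uses 30.
- Last blinded infusion: Visit 14, infusion 12.
- Assumption: the first open-label infusion is at Visit 15, one interval after Visit 14.

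**The plan's own timing figures reproduce**
- Maximum initial period of 228 days: 6 × (28 + 10) = 228. The longest interval consistent with the plan is therefore 38 days.
- Visit 16 at day 390: 330 + 60 = 390, and 360 + 30 = 390.

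**Formula for interval d, counting from the Visit 12 infusion**
- Last blinded infusion at 2d, so the Period 3 window is 2d + 60.
- Open-label start at 3d, so the overlap is (2d + 60) − 3d = 60 − d.
- Share of Period 3 = (60 − d)/(2d + 60).

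| d (days) | Window | Overlap | Share |
|---|---|---|---|
| 21 | 102 | 39 | 38% |
| 28 | 116 | 32 | 28% |
| 30 (target grid) | 120 | 30 | 25% |
| 38 | 136 | 22 | 16% |

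**Variations on the target grid**
- Whole-study non-switch placebo window: 11 × 30 + 60 = 390 days, and 30/390 = 7.7%.
- Open-label start 10 days after day 360: 20/120 = 17%. Start 30 days after: 0%.
- Three blinded unscheduled infusions at 30-day spacing: the window is 120 + 90 = 210 days, the overlap is still 30, and 30/210 = 14%.
- If all 20 planned non-switch placebo patients roll over on schedule: 20 × 30 = 600 of 20 × 120 = 2,400 Period 3 patient-days.

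**With the cut in place:** a rollover patient's Period 3 window is day 270 to day 359, about 90 days, with none of it on open-label drug. A patient who does not roll over keeps 120 days.

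**The case against.** The strongest reply is that the data for misattribution may never reach this trial. SAP 5.4.1 classifies events recorded on the CRF. Protocol 14.1 itself runs adverse-event assessment through the final visit. Four places (Synopsis, 11.2, 11.5.6, 15.2) limit later follow-up to patients who do not continue, and the open-label study has its own consent. The sentence in 14.1 about all subjects uses the same 30-day and 60-day terms as Visit 16 and may simply describe it. This stands as a limit on size: the 25% is window time, not a share of events. It does not remove the gap, because 14.1 says all subjects and the SAP's rule would count whatever is recorded.

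It can also be said that SAP 5.4.1 summarises events by treatment received and allocates them to the period of last treatment. That shows the intent, but the open-label study is not one of the three periods, so these rules do not reach it.

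Two stronger readings are tempting. A reader might infer that a real EDS-EP excess would be hidden. The documents do not establish that any open-label event enters these tables, and SAP 5.4 plans no statistical comparison between groups for safety. Period 1, the main placebo-controlled safety comparison, is cut correctly. A reader might also infer that, if rollover events stay in the open-label database, unequal window lengths bias the arms. That would need rollover rates to differ by arm. Rollover is offered on the same terms to all arms with extension assignments kept blinded, and nothing in the documents shows such a difference. The proposed cut would itself leave rollover patients with the shorter window.

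**Conclusion.** The gap in the rule is real: nothing in SAP 5.4.1 closes Period 3 at the first open-label infusion. On target days, with open-label dosing at Month 12, 30 of 120 Period 3 days (25%) fall on open-label EDS-EP, with a range of 16% to 38% over intervals of 38 to 21 days. This is about 8% of the whole-study non-switch placebo window. It shrinks with a later open-label start or with blinded unscheduled infusions, and vanishes if open-label starts more than 60 days after the last blinded dose.

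The consequence is conditional. Any event recorded in the overlap is attributed to non-switch placebo or low dose. How many such events exist depends on which of Protocol 14.1 and the non-continuer-only passages governs. The effect is on attribution in descriptive tables with about 20 planned placebo patients, not on any test. Bias between arms from unequal windows is not shown.

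Protocol 16.2.8 and item 4 of SAP 5.1.8 describe a 1:1 allocation of remaining placebo patients to the two dose ranges in the open-label study, whereas Protocol 7.3 gives everyone the high range. Those passages must be reconciled. For placebo patients the overlap is with active drug on either reading, but the low-dose part of this point rests on Protocol 7.3.

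**What to change.** 1. In SAP 5.4.1, end Period 3 at whichever comes first: 60 days after the last blinded infusion (counting any blinded unscheduled infusion), or the start of the first infusion in IEDAT-03-2018. Use the same end point for the Entire Study tables, which begin at the first infusion.
2. Reconcile Protocol 14.1 with the Synopsis, 11.2, 11.5.6 and 15.2 on whether rollover patients are followed for adverse events after Month 12 and in which study's database those events are recorded. Align the SAP Introduction's definition of Period 3.
3. Report patient-days at risk by group beside the percentages, because windows will still differ by rollover (about 90 against 120 days on target days).

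The cost is one SAP sentence, one added date variable (first open-label infusion), a patient-days line in the tables, and slightly shorter follow-up for rollover patients.
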